13.	Adverse events, serious adverse events and device deficiencies	34
13.1.	Adverse events	34
13.2.	Adverse device effect	34
13.3.	Device deficiency	34
13.4.	Serious adverse events	34
13.5.	Medical care of subjects	35
13.6.	Reporting and timelines	35
14.	Suspension or premature termination of the clinical investigation	37
15.	Clinical investigation report	38
16.	Publication policy	39
16.1.	General	39
17.	Bibliography	40

TABLE OF TABLES

Table 1 Study period including three (3) visits, Healthy volunteers..... 15

Table 2 Study period including two (2) visits, SCI and BPH patients 15

Table 3 Estimated timeline of the investigation 19

Table 4 chart showing the connection between visits and assessments for Healthy volunteers 22

Table 5 chart showing the connection between visits and assessments for SCI and BPH patients..... 23

Table 6 Anticipated adverse device effects and their likely incidence rates..... 34

TABLE OF FIGURES

Figure 1 Two examples of how to make corrections in the CRF 24

SYNOPSIS OF THE CLINICAL INVESTIGATION

Objective

The aim of the study is to explore and understand how urodynamic parameters are affected when emptying the bladder with an intermittent catheter in healthy volunteers, patients with Spinal Cord Injury (SCI) and patients with enlarged prostate (BPH).

The primary objective is to investigate the urodynamic parameters in healthy volunteers emptying spontaneously and with an intermittent catheter (IC).

Secondary objective is to evaluate the urodynamic parameters in spinal cord injured patients as well as patients with enlarged prostate emptying their bladder with an intermittent catheter (IC).

Endpoints

Due to the explorative nature of the study, no primary endpoint is defined but endpoints are divided into three categories dependent on their relation to bladder, urethra or urine.

[REDACTED]

[REDACTED]

[REDACTED]

[REDACTED]

[REDACTED]

- [REDACTED]

Additionally

- Discomfort during catheter insertion and withdrawal on a Visual Analogue Scale
- Adverse events

Pass/fail criteria

The study will provide valuable insight into the development of pre-clinical models but no formal success criteria are applied in this exploratory study.

Design of the investigation

The investigation is conducted at one site and is an explorative study, estimated to last three months. The investigation is an open single arm investigation including 30 male subjects. 10 healthy volunteers, 10 patients with Spinal Cord Injury (SCI) and 10 patients with enlarged prostate (BPH).

The healthy volunteers included into the study will have three visits – an inclusion visit, a study visit including measurement of endpoints while spontaneous voiding of the bladder followed by a last visit measuring endpoints while emptying the bladder using a standard IC.

The subjects with SCI and BPH will have two visits. – the first visit includes a urine culture analysis and prophylactic antibiotic is prescribed per the result of the analysis. (Most IC users have bacteria in the urine and to

decrease the risk of acquiring a urinary tract infection from the urodynamic examination, urine cultures are performed and prophylactic antibiotics will be prescribed per the result). The second visit is conducted while the patient is on antibiotic treatment and includes a urodynamic examination measuring all endpoints while emptying the bladder with a standard IC.

Population

The investigational population consists of healthy subjects, patients with SCI and patients with BPH who comply with the following inclusion and exclusion criteria:

Inclusion criteria

- Have given written informed consent and signed letter of authority
- Be at least 18 years of age and have full legal capacity
- Be a male

Healthy volunteers only,

- Have a negative urine multistix:
 - Leukocytes
 - Nitrite

Or if positive, subsequent negative for bacterial growth in urine culture

- Willing to refrain from using analgesics up to 24 hours prior to catheterization visits

The two patient populations only,

- Use IC daily due to SCI or BPH and have used IC for at least 2 months

Exclusion criteria:

- Symptoms of urinary tract infections
- Have previously participated in this investigation
- Participate in other clinical investigations related urinary tract system during this investigation
- Known hypersensitivity toward any of the test products

Healthy volunteers only:

- Abnormalities, diseases or surgical procedures performed in the lower urinary tract (inclusion to termination).

Test products

The purpose of the investigation is to obtain urodynamic data while emptying the bladder [REDACTED] and therefore, no investigational devices are being investigated.

Investigation approval

1.3. Other

All delegated investigation tasks from Investigator to Study Nurses will be documented in the Site Personnel Signature and Delegation List.

2. Identification and description of the investigational device

The purpose of the investigation is to obtain urodynamic data while emptying the bladder [REDACTED] and therefore, no investigational devices are being investigated.

3. Justification for the conduct of the clinical investigation

Intermittent catheterisation is the preferred method of bladder emptying for persons with spinal cord injuries and neurogenic bladder dysfunction (1). Coloplast manufactures intermittent catheters and works continuously to improve them. During the development of new intermittent catheters, lab models are used to screen new catheter prototypes.

The data from the investigation will be compared to lab data [REDACTED]

4. Investigational device and clinical investigation risks and benefits

Risks associated with the investigation may be discomfort or stinging in the urethra during the urodynamic examination and the catheterisation. Furthermore, there may be a risk of micro trauma and haematuria after catheterisation, which heals within 1-3 days. After a urodynamic examination, there may be a risk of obtaining a urinary tract infection.

4.1. Anticipated clinical benefits

The clinical investigation is conducted in accordance with "The Declaration of Helsinki, 1964, last amended at the 64th WMA General Assembly, Brazil, October 2013".

By participating in this investigation, the subjects will contribute with important data for developing novel lab models that can simulate bladder emptying and be used to develop improved intermittent catheters.

The risks and disadvantages of participating in the investigation are estimated to be low. The healthy subjects will not have any benefits from this investigation, but it may in the future benefit individuals who are dependent on intermittent catheters for emptying their bladder.

4.2. Possible interactions with concomitant medical treatments.

There is no known interaction between the planned study procedures and concomitant medication.

5. Objectives and hypotheses of the clinical investigation

5.1. Objective

The aim of the study is to explore and understand how urodynamic parameters are affected when emptying the bladder with an intermittent catheter in healthy volunteers, patients with Spinal Cord Injury (SCI) and patients with enlarged prostate (BPH).

The primary objective is to investigate the urodynamic parameters in healthy volunteers emptying spontaneously and with an intermittent catheter (IC).

Secondary objective is to evaluate the urodynamic parameters in spinal cord injured patients as well as patients with enlarged prostate emptying their bladder with an intermittent catheter (IC).

6. Design of the clinical investigation

6.1. General

The investigation is an explorative open single arm investigation including 30 male subjects. 10 healthy volunteers, 10 patients with SCI and 10 patients with BPH.

The healthy volunteers included into the study will have an information visit and three study visits – an inclusion visit (visit 0), a visit 1 measuring endpoints while spontaneous voiding of the bladder (0-7 days after visit 0) followed by a visit 2 measuring endpoints while emptying the bladder using a standard IC (4-15 days after visit 1). (Visit 0 and visit 1 can be the same day).

The subjects with SCI and enlarged prostate will have an information visit and two study visits. – an inclusion visit (visit 0) where a urine culture is analysed and prophylactic antibiotic is prescribed per the result of the analysis. (Most IC users have bacteria in the urine and to decrease the risk of acquiring a urinary tract infection from the urodynamic examination, urine cultures are performed and prophylactic antibiotics will be prescribed per the result). The second visit (visit 1) is conducted while the patient is on antibiotic treatment measuring all endpoints while emptying the bladder with a standard IC (4-15 days after visit 0 while subject is on prophylaxis antibiotics).

The investigation is conducted at one site and is an explorative study, estimated to last eight (8) months.

Table 1 and 2 illustrates the study period and the adherent study activities performed at each visit for the healthy volunteers, the SCI and BPI patients respectively.

Visit	Process	Activity
-	Study Information	
 • Subject Information
0	Inclusion	
 • Informed Consent Form • In- and exclusion criteria fulfilled • Urine multistix performed (leukocytes, nitrite and erythrocytes) • Baseline data collected and entered in the CRF by nurse • Relevant concomitant medication recorded • Schedule visit 1 (may be same day as visit 0)
1	Endpoints measured during normal voiding	
 • Check for use of analgesics and symptoms of UTI (and urine multistix performed if visit 1 is not the same day as visit 0) • [REDACTED] • [REDACTED] • Standard Urodynamic examination performed (twice, first measuring is for adjustment and second measurement is recorded) • Registration of any adverse events and relevant concomitant medication • Schedule visit 2
2	End points measured during bladder emptying with IC	
 • Check for use of analgesics and symptoms of UTI (and urine multistix performed) • Special Urodynamic examination including flowrate performed (one measurement). Catheters to be used is one standard and one RIK catheter • One hour break • [REDACTED]

- Discomfort registered by subject on a Visual Analogue Scale
- Registration of any adverse events and relevant concomitant medication
- Termination form

Table 1 Study period including three (3) visits, Healthy volunteers

Visit	Process	Activity
-	Study Information	
 • Subject information
0	Inclusion	
 • Informed Consent Form • In- and exclusion criteria fulfilled • Baseline data collected and entered in the CRF by nurse • Relevant concomitant medication recorded • Urine multistix recorded, urine culture performed and antibiotic prescribed per bacteria present • Schedule visit 1 (during treatment with antibiotic) 5-14 days after visit 0
1	Catheterisation with test product 1	
 • Check for symptoms of UTI (and urine multistix performed) • Special Urodynamic examination including flowrate performed (one measurement). Catheters to be used is one standard and one RIK catheter (for SCI pts an extension tube shall be used). • One hour break • Discomfort registered by subject (if possible) on a Visual Analogue Scale • Registration of any adverse events and relevant concomitant medication • Termination form

Table 2 Study period including two (2) visits, SCI and BPH patients

6.1.1. Endpoints

Due to the explorative nature of the investigation, no primary endpoint is defined but endpoints are divided into three categories dependent on their relation to bladder, urethra or urine.

The statistical analysis to be performed on the explorative endpoints is described in Section 7.

[REDACTED]

[REDACTED]

[REDACTED]

[REDACTED]

[REDACTED]

[REDACTED]

[REDACTED]

[REDACTED]

[REDACTED]

Discomfort measured during:

- Catheter insertion measured by subjects on a Visual Analogue Scale, VAS scale: On a scale ranging from "no discomfort" to "worst possible discomfort comfort" caused by the catheter, set a vertical line indicating how you experienced the insertion of the catheter
- Catheter withdrawal measured by subjects on a Visual Analogue Scale, VAS scale: On a scale ranging from "no discomfort" to "worst possible discomfort comfort" caused by the catheter, set a vertical line indicating how you experienced the withdrawal of the catheter

Safety data

- Adverse events

6.1.2. Baseline / Demographic data

The following baseline data is collected:

- Age
- Collection of urine samples for analysis for:
 - pH
 - Protein
 - Viscosity
 - Osmolality
 - Bacteria level
- Bladder wall condition (normal thickness, increased thickness, other, unknown)

For SCI and BPH pts:

- Reason for using IC
- Bacteria level on IC catheter used for collecting urine sample (using subject own catheter)
- Time using IC
- Number of catheterisations a day
- Brand name of catheter
- Possible to void spontaneously

6.1.3. Rationale for selection and measurement of endpoints

Intermittent catheterisation is the preferred method of bladder emptying for persons with spinal cord injuries and neurogenic bladder dysfunction. Coloplast manufactures intermittent catheters and works continuously to improve them. During the development of new intermittent catheters, lab models are used to screen new catheter prototypes.

6.1.4. Discussion of clinical investigation design

As no investigational product is investigated and the investigation is of explorative nature, the design is an open single arm investigation.

During the investigation, there must be 4-15 days between each study visit. The minimum period is set to allow potential micro trauma from study procedures to heal. The maximum period is set to meet logistical requirements in planning subjects' visits.

To explore and understand how urodynamic parameters are affected when emptying the bladder with an intermittent catheter in healthy volunteers, patients with SCI and patients with BPH, male subjects are chosen

Many IC users have bacteria in the urine and to decrease the risk of acquiring a urinary tract infection from the urodynamic examination, urine cultures are performed and prophylactic antibiotics will be prescribed per the result.

6.2. Subjects

To be included in the investigation, the subjects must comply with the selection criteria described in section 6.2.1 and 7.

6.2.1. Inclusion criteria for subject selection

Subjects interested in participating the clinical investigation must comply with the following criteria:

1. Have given written informed consent
2. Be at least 18 years of age and have full legal capacity
3. Be male
4. For healthy volunteers: Willing to comply with not using analgesics up to 24 hours prior to study visit
5. For healthy volunteers: Negative urine multistix (leukocytes and nitrite), or if positive, subsequent negative for bacterial growth in urine culture
6. For SCI and BPH patients: Use intermittent catheter daily and have used intermittent catheters for at least 2 months

Justification for inclusion criteria

1. To meet the Helsinki declaration
2. To meet the Helsinki declaration
3. To ensure data can be used to resembling the lab models with are using male pig urethras
4. Pain relief can affect endpoint related to discomfort.
5. To ensure the subject does not have a urinary tract infection at inclusion
6. To ensure data can be used to resembling the lab models
7. To ensure data can be used to resembling the lab

6.2.2. Exclusion criteria for subject selection

Subjects complying with the following criteria must be excluded from participation in the clinical investigation:

1. Symptoms of urinary tract infections (frequent urination, stinging and pain at urination)
2. Participate in other clinical investigations related to urinary tract system during this investigation (Inclusion → termination)

3. For healthy volunteers: Abnormalities, diseases or surgical procedures performed in the lower urinary tract

Justification for exclusion criteria

1. To ensure that the subjects do not have urinary tract infection at inclusion. None of the symptoms may be present.
2. Other investigation guidelines/procedures may interfere with these investigational endpoints.
3. To ensure homogeneous group of urinary tracts where abnormalities, diseases or surgical procedures do not have an influence on measured parameters.

6.2.3. Recruitment and enrolment

Recruitment of potential subjects will begin once approvals have been obtained from the Ethics Committee of the Capital Region Denmark.

Recruitment will take place using subject records from the site as well as from Coloplast own subject database [REDACTED], www.forsøgsperson.dk and, if necessary, through advertisements in local newspapers.

Only users of intermittent catheter are registered in the Coloplast database, which after their initial registration have given oral consent to receive material about clinical investigations from Coloplast will be approached.

- Potential subjects are identified by the following search criteria in the Coloplast database: Be at least 18 years of age and have full legal capacity
- Be male
- Use intermittent catheter daily due to spinal cord injury or enlarged prostate
- Used IC for a period of at least 2 months

The identified potential subjects from the Coloplast User Database will receive by mail or email, the Subject Invitation Letter with the written subject information and "Forsøgspersoners rettigheder i et sundhedsvidenskabeligt forskningsprojekt" attached. If the subject is interested in participating, he is encouraged to contact the site and an information meeting is arranged.

Investigator identifies potential subjects in relation to in- and exclusion criteria, through subject records kept at the site (from previous clinical studies involving healthy subjects). The identified potential subjects will receive an Invitation Letter with the written subject information and "Forsøgspersoners rettigheder i et sundhedsvidenskabeligt forskningsprojekt" attached. If the subject is interested in participating, he is encouraged to contact the site and an information meeting is arranged.

Subjects may furthermore be recruited through www.forsøgsperson.dk where potential subjects can gather information on clinical studies. If necessary, they may also be recruited through local newspapers. Interested potential subjects contact the Clinical Manager at Coloplast or a representative hereof. In- and exclusion criteria are reviewed and general questions regarding the study are answered. If the potential subject is interested in participating, he will receive the written subject information and "Forsøgspersoners rettigheder i et sundhedsvidenskabeligt forskningsprojekt" and contact information is passed on to investigator or study nurse, who will contact the potential subject. If he still wishes to participate, an information meeting is arranged.

Potential subjects recruited in one of the above ways will, at visit 0, go through the informed consent process. Once enrolled in the study, the subject may then continue to in- and exclusion.

The informed consent process is described in Section 12.

6.2.4. Subject withdrawal criteria

The subject can withdraw from the investigation at any time for whatever reason without any consequences for their future treatment outside the clinical investigation.

Investigator may withdraw a subject from the investigation at any time if they judge it to be the subject's interest.

The investigator must withdraw a subject from the investigation due to:

- Noncompliance with the CIP impacting the scientific integrity of the investigation.
- If subject's safety and wellbeing is compromised by further participation.

Withdrawn subjects will not be replaced by new subjects.

A subject who is withdrawn from the investigation, for any reason, will be encouraged to contact the investigator if problems arise that he believes are related to the investigation. A subject who has not experienced adverse events will not be followed up. For subjects who experience adverse events, see section 14. At termination, due to above reasons investigator or study nurse completes the termination form and sponsor is informed.

6.2.5. Point of enrolment

A subject is considered enrolled in the investigation when the written informed consent is obtained. The expected duration for each subject is described in section 6.1.

6.2.6. Total expected duration of the clinical investigation

The dates below are approximate and no subjects will be enrolled before the required approval from Ethics Committee of the Capital Region Denmark have been obtained. Changes greater than ± 2 months will be notified to EC.

Activity	Estimated time
First subject enrolled	November 2017
Last subject enrolled	May 2018
Last subject completed	June 2018
Final Report	June 2019

Table 3 Estimated timeline of the investigation

The investigation is terminated when the last subject has ended his participation. The same committee and authority will be informed of investigation termination within 90 days hereof (unless the investigation is terminated prematurely where information is given 15 days after termination, including the reason for premature termination).

6.2.7. Total number of subjects

During the investigation period, there will be enrolled 30 subjects. A subject is considered enrolled in the investigation when he has signed and dated the Informed Consent Form.

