6.3. Procedures

6.3.1. Clinical investigation-related procedures

Before initiation of the clinical investigation, sponsor must be provided with key personnel signed and dated curriculum vitae (not more than 2 years old) to verify their qualifications. Key site personnel are those, who treat or evaluate subject data in the clinical investigation. Also, the sponsor will ensure that all site personnel are trained in the investigation procedures, how to complete the CRFs, procedure for reporting an adverse event or serious adverse event (how, when, to whom), and who to contact in case of emergency related to the investigational device.

Study period

Healthy Volunteers:

During the study period, each subject of the healthy volunteers has an information visit and three (3) study visits: Visits 0, 1 and 2. Visit 0 and visit 1 can be the same day.

Information Visit:

Subject will be given information about the investigation by the investigator and have a minimum of 24 hours before deciding on participating in the investigation.

Visit 0 (Inclusion):

Subject will sign the Informed Consent Form (see section 12). It is then ensured that in- and exclusion criteria are met, including urine analysis with multistix, leukocytes and nitrite (Multistix 7, Siemens). Enrolled subjects are allocated a subject number, and hereafter demographics, baseline data and concomitant medication is recorded. A urine sample is collected for baseline data analysis performed by Coloplast laboratory.

Visit 1, 0-7 days after last visit (Normal Voiding):

Subject is asked about symptoms for urinary tract infections (frequent urination, stinging or pain at urination) and a urine analysis with multistix, leukocytes and nitrite (Multistix 7, Siemens) is performed. The subject is asked about use of analgesics up to 24 hours prior to the visit and if the multistix analysis is showing negative in leukocytes and nitrite and there are no symptoms of urinary tract infection and no use of analgesics, the subject will continue with the standard urodynamic examinations (measured twice, first measuring is for adjustment and second measurement is recorded), [REDACTED].

The nurse register relevant data in the CRF, including possible adverse events and relevant concomitant medication. Next visit is scheduled.

Visit 2, 4-15 after last visit (IC)

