Subject is asked about symptoms for urinary tract infections (frequent urination, stinging or pain at urination) and a urine analysis with multistix, leukocytes and nitrite (Multistix 7, Siemens) is performed. The subject is asked about use of analgesics up to 24 hours prior to the visit and if the multistix analysis is showing negative in leukocytes and nitrite and there are no symptoms of urinary tract infection and no use of analgesics, the subject will continue with the special urodynamic examination [REDACTED]

In addition, the subject evaluates the discomfort of the insertion and withdrawal of the intermittent catheter using a VAS scale.

The nurse register the subject evaluation and other relevant data in the CRF, including possible adverse events and relevant concomitant medication.

[REDACTED]

The subject has completed the investigation and the termination form is completed.

SCI and BPH patients:

During the study period, each subject of the SCI and BPH population has an information visit and two (2) study visits: Visits 0 and 1.

Information Visit:

Subject will be given information about the investigation by the investigator and have a minimum of 24 hours before deciding on participating in the investigation.

Visit 0 (Inclusion):

Subject will sign the Informed Consent Form (see section 12). It is then ensured that in- and exclusion criteria are met, including urine analysis with multistix, leukocytes and nitrite (Multistix 7, Siemens). Enrolled subjects are allocated a subject number, and hereafter demographics, baseline data and concomitant medication is recorded. A urine culture is performed and antibiotics is prescribed per bacteria present and a urine sample is collected for baseline data analysis performed by Coloplast laboratory. Next visit is scheduled.

Visit 1, 4-15 days after visit 0 (IC):

Subject must be on prescribed prophylaxis antibiotic and is asked about symptoms for urinary tract infections (frequent urination, stinging or pain at urination). A urine analysis with multistix, leukocytes and nitrite (Multistix 7, Siemens) is performed and if there are no symptoms of urinary tract infection, the subject will continue with the special urodynamic examination [REDACTED].

In addition, the subject evaluates the discomfort of the insertion and withdrawal of the intermittent catheter using a VAS scale.

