10.2. Violations

Violations to the Clinical Investigation Plan occurs when there is divergence from the EC approved investigation plan (a deviation) that also:

- Reduces the quality or completeness of the data
- Impacts a subject's safety, rights or wellbeing
- Affects the scientific integrity

Examples of violations:

- Inadequate informed consent
- Enrolment of subjects not meeting the inclusion / exclusion criteria
- Initiation of study procedure prior to completion of informed consent
- Unreported SAE's
- Repeated deviations of the same nature
- Falsification

If any deviations and/or violations to the investigation plan are detected, the Clinical Manager will complete a Deviation/Violation Form and inform/discuss with the Principal Investigator immediately.

In case of continued or repeated violations affecting the scientific aspect of the investigation or the subjects' rights, safety and well-being sponsor will disqualify the PI from further participation in the investigation.

The Clinical Manager must report all violations detected during a monitoring visit in the Periodic Monitoring Report.

11. Statement of compliance

The clinical investigation is conducted in accordance to:

- Ethical principles that have their origin in "The Declaration of Helsinki, 1964, last amended at the 64th WMA General Assembly, Brazil, October 2013".
- MDD 93/42/EEC as amended by Directive 2007/47/EC (commonly known as the Medical Device Directive).
- ISO 14155:2011 "Clinical Investigation of medical devices for human subjects – Good clinical practices".
- Any applicable regional or national regulations will be specified in the country specific CIP.

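### Does counting the 30 subjects at signed consent, before the eligibility check, put the 10 per group at risk?

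*Combined protocol and SAP*

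**What the plan says.** All references are to the combined protocol and SAP.

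**Counting at consent.** Section 6.2.7 gives the total and the definition together: "there will be enrolled 30 subjects. A subject is considered enrolled in the investigation when he has signed and dated the Informed Consent Form". Section 6.2.5 repeats the definition without a number: "A subject is considered enrolled in the investigation when the written informed consent is obtained". Section 6.2.3 confirms the order: "Once enrolled in the study, the subject may then continue to in- and exclusion".

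**Eligibility after consent.** For all three groups, section 6.3.1 has the man sign at visit 0 and then says "It is then ensured that in- and exclusion criteria are met, including urine analysis with multistix". The next sentence reads "Enrolled subjects are allocated a subject number, and hereafter demographics, baseline data and concomitant medication is recorded".

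**Group sizes.** Section 6.1 describes a study including 30 men, 10 per group. Section 7.2 reports no formal sample size calculation and assumes that 10 per group is adequate for characterization. Sections 6.2.4 and 7.4 do not replace withdrawals or drop-outs; neither mentions screen failures.

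**Other uses of the terms.** In section 7.1 the ITT population is drawn from included subjects who also have valid consent and at least one valid endpoint, while the safety population is defined by consent alone. Section 10.2 gives as one example of a violation "Enrolment of subjects not meeting the inclusion / exclusion criteria".

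**The concern.** Read literally, 6.2.7 stops recruitment at 30 signatures, and every man who then fails the visit 0 check takes one of the 10 places in his group. Failure after consent is possible in all three groups. Section 6.2.2 excludes any man with "Symptoms of urinary tract infections (frequent urination, stinging and pain at urination", and Tables 4 and 5 put that question at visit 0. Healthy men face a further criterion in 6.2.1: "For healthy volunteers: Negative urine multistix (leukocytes and nitrite), or if positive, subsequent negative for bacterial growth in urine culture".

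Elsewhere the vocabulary seems to point the other way. Subject numbers go to enrolled men in a sentence placed after the criteria check, and the 10.2 example makes sense only if enrolment implies eligibility. If the consent definition were carried into 10.2, an ordinary screen failure might look like a reportable violation.

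At stake would be a group of fewer than 10, and a site unsure when to stop recruiting and what to report.

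**Working it through.** **1. The plan's own figure.** 10 + 10 + 10 = 30, so the total reproduces. With no formal calculation in 7.2, there is no effect size, SD or power to recompute.

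**2. What each section says about the 30.**

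| Section | Mentions 30? | Bearing on the count |
|---|---|---|
| 6.2.7 | yes | counted at consent |
| 6.2.5 | no | enrolment is at consent |
| 6.2.3 | no | enrolment comes before the criteria check |
| 6.1 | yes | men *included*, but the same paragraphs give the included volunteers an information visit and an inclusion visit, so the word is loose |
| 6.3.1 | no | *enrolled* follows the criteria check; it can mean eligible men or all who signed |
| 7.1, ITT | no | *included* is not the same as consented |
| 7.1, safety | no | consent alone, in agreement with 6.2.5 |
| 10.2 | no | one example in a list, not a definition of enrolment |

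Only 6.1 sets a count of 30 beside the one in 6.2.7, and it does not say that those 30 have passed the criteria. What remains is silence on one point: whether a screen failure occupies a place.

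**3. Does 10.2 turn a screen failure into a violation?** Section 10.2 first requires a divergence from the approved plan, and then an effect on data, on the subject or on scientific integrity. A man who signs, is checked and is turned away has been handled as 6.2.3 and 6.3.1 direct. Nothing has diverged, so the first condition is not met.

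**4. Cost if the site stops at 30 consents.** The documents give no screen-failure rate, so the effect is shown per failure. The 95% half-width for a group mean, in SD units, is t(0.975, n−1)/√n:

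- n = 10: 2.262/3.162 = 0.715
- n = 9: 2.306/3 = 0.769, which is 0.7687/0.7154 = 1.075, or 7.5% wider
- n = 8: 2.365/2.828 = 0.836, which is 0.8360/0.7154 = 1.169, or 16.9% wider

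At an assumed failure rate f of 5% or 10%, the expected number eligible per group is 10(1 − f) = 9.5 or 9.0. The chance that all 10 pass is 0.95^10 = 0.60 or 0.90^10 = 0.35.

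**5. Cost if the site recruits to 10 eligible men per group.** Consents per group are 10/(1 − f), rounded up within the group because the target is per group:

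- f = 5%: 10/0.95 = 10.5, so 11
- f = 10%: 10/0.90 = 11.1, so 12

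If failures occur in all groups, this is 3 × 11 = 33 to 3 × 12 = 36 consents. If they occur only among healthy men, it is 20 + 11 = 31 to 20 + 12 = 32. The excess over 30 is 1 to 6 signatures and visit 0 checks. No more than the planned 30 men go on to urodynamic examination.

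**The case for a change.** The strongest case for a change is that either literal course causes trouble. Stopping at 30 signatures leaves a group short after any failure. Consenting a 31st man exceeds the number in 6.2.7, and 10.1 treats a departure from the approved plan as a deviation. The no-replacement rules in 6.2.4 and 7.4 do not settle the matter, because they concern men who withdraw or drop out. One sentence would remove the doubt.

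Part of this stands. The documents do not state the rule, and failure after consent cannot be ruled out. The route is narrower than it looks, though. Section 6.2.3 has candidates from site records identified against the criteria, and has the criteria reviewed for website and newspaper candidates before the information meeting. A positive multistix alone does not exclude a healthy man, since a negative culture makes him eligible. No section forbids approaching another man after a screen failure. Section 6.4 also keeps the sponsor in close contact with the site during recruitment to resolve such problems.

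The precision argument is weaker. The visible text of 7.1 plans summaries and listings by group, with no interval for a group mean and no precision target. A move from 0.72 to 0.77 SD therefore misses no stated requirement.

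**Conclusion.** The concern identifies a real ambiguity but not a defect that calls for a change. Section 6.2.7 counts at consent, 6.1 and 7.2 think in groups of 10, and the plan does not link the two. This is a gap that a site and sponsor fill sensibly during recruitment.

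On the strict reading, the loss is one man's data per screen failure, about 7.5% in half-width for the first failure in a group and 16.9% for two. On the practical reading, it is roughly 1 to 6 extra consents. Neither reading introduces bias, alters a power or type I error statement, or changes an analysis population: the ITT set still needs a valid endpoint, and the safety set still rests on consent. Section 10.2, by its own definition, does not catch a properly handled screen failure.

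The consent figures rest on an assumed failure rate of 5% to 10%. The conclusion does not, because it depends on the study being descriptive, with 10 per group an assumed round number rather than a calculated minimum. A substantially higher failure rate combined with a strict stop at 30 signatures would thin the groups further: at an assumed 20%, 10 × 0.80 = 8 per group would be expected. The result would still be a valid description of a smaller sample.
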